7.13 Other Therapy Guidelines

All other therapies administered for both hypothermia and normothermia groups during the times corresponding to initial cooling, hypothermia maintenance, and rewarming periods will be according to the clinical care team.

8 Study Data Collection

Clinical data will be collected at the time of enrollment, throughout the intervention period, during the initial hospital stay and at the time of hospital discharge or death. Follow-up information including assessment of neurobehavioral outcomes will be collected at three and 12 months. This section provides a summary of the data that will be collected.

8.1 Screening, Enrollment and Randomization Period

Patients will be screened by the clinical investigator in the emergency department and in-hospital settings. Parents or legal guardians of potential subjects will be asked for permission to enter the trial, and the subject will be enrolled and randomized within six hours of ROSC/ROC. During this period patients will be evaluated for inclusion and exclusion criteria and demographic information will be collected. Demographic information will include: date of birth, gender, race, and ethnicity. If the patient meets all

inclusion and exclusion criteria and consent is obtained, the patient will be randomized into the study.

8.2 Baseline Period

Baseline data elements will be collected on all patients who have been enrolled and randomized into the study. Information to be collected during this period include a medical and surgical history, a physical examination, hospital and PICU admission information, cardiac arrest information, vital signs, evaluation of mental status, and infection status. Safety laboratories to measure serum chemistry, coagulation parameters, and hematologic parameters will also be collected at baseline.

8.3 Intervention Period (0 to 120 Hours)

Study interventions will begin after randomization. During the intervention period, vital signs will be monitored for all patients. Safety laboratories to measure serum chemistry, coagulation parameters, and hematologic parameters will also be collected. Information on daily chest x-rays will also be collected. Chest x-rays are performed routinely on patients after cardiac arrest to assess for signs of new infiltrates and to determine proper positioning of tubes including the esophageal temperature probe. The results of all blood, urine and respiratory cultures during the intervention period will be recorded. Adverse events, concomitant medications, and procedures and therapies administered will be recorded for both groups.

8.4 Post Intervention Through Discharge

After the intervention period, patients will be monitored according to standard PICU clinical practice for the participating site. Patients will be reviewed daily for their minimum and maximum temperatures through day 10 or hospital discharge, whichever is earlier. The results of all blood, urine and respiratory cultures conducted up to seven days after cardiac arrest will be recorded. Concomitant medications will be recorded from the time of randomization through day 7. Select procedures and therapies will be recorded through hospital discharge. Blood products received within seven days of arrest will be recorded. Adverse events will be recorded from the time of randomization through Day 14. Adverse events that have not resolved by Day 14 will be followed until resolution or hospital discharge, whichever is earlier. If the Adverse Event has not resolved at the time of hospital discharge, the Research Team should follow the guidelines for AE follow-up outlined

in section 11.2.6 of the protocol. PICU and hospital discharge information will be captured.

8.5 Day 28 Status

The vital status of the patient will be recorded on day 28. If the patient has been discharged to home prior to day 28, the parents may be contacted if all other efforts to determine patient mortality have been exhausted.

8.6 Three Month Follow Up

Caregivers will be contacted at three months post arrest and will be asked the status of the patient, location of the patient, and if the patient has undergone any additional procedures or therapies. The caregiver will be asked to provide information on family burden, the patient's global function, POPC, and PCPC. The VABS-II assessment will be done at this time. If the respondent is the child's treating healthcare professional the information on family burden will not be collected. All telephone follow up at three months will be conducted centrally by staff at the Kennedy Krieger institute (Johns Hopkins School of Medicine, Baltimore, MD) to assure uniform performance of the VABS-II assessment. In order to assess interrater reliability of the VABS II telephone interviews, and prevent variance in ratings over time, a subset of interviews (every 10th interview) will be recorded. Recorded interviews will be reviewed and rescored by [name]. Discrepant scores will be adjudicated through discussion between [name] and the psychometrician.

The three month follow up has several purposes. First, the contact will help with subject retention by maintaining communication with the family. Second, the three month assessment will be used to test our primary endpoint conclusions for robustness with respect to missing data (see Section 9.2 on Page 59). Third, it is of exploratory interest to determine if there is a trajectory of improvement between three months and 12 months.

8.7 12 Month Follow Up

Parents will be contacted at 12 to 16 months post arrest and will be asked the status of the patient, location of the patient, and if the patient has undergone any additional procedures or therapies. The parents will be asked to provide information on family burden, the patient's global function, POPC, PCPC, and VABS-II assessment. In addition to measures administered over

the phone, the patient will have a neuropsychological evaluation and neurological assessment performed at the study site at 12 to 16 months post arrest.

All telephone follow up will be conducted centrally by staff at the Kennedy Krieger Institute (Johns Hopkins School of Medicine, Baltimore, MD). In order to assess interrater reliability of the VABS II telephone interviews, and prevent variance in ratings over time, a subset of interviews (every 10th interview) will be recorded. Recorded interviews will be reviewed and rescored by [name]. Discrepant scores will be adjudicated through discussion between [name] and the psychometrician.

9 Data Analysis

9.1 General Analytic Issues

THAPCA will be analyzed according to the intention to treat principle, wherein all subjects randomly assigned to a treatment arm will be counted in that arm regardless of adherence to protocol or possible crossover to the other treatment arm. Therefore, this clinical trial will assess whether an initial strategy of hypothermia leads to different rates of death or poor neurological outcome than an initial strategy of normothermia. As THAPCA consists of two separate clinical trials, the alpha level for analysis of each trial is 0.05. All tests will be two-tailed.

9.2 Primary Analysis

The primary endpoint of each THAPCA trial is survival with good neurobehavioral outcome at 12 months post arrest. The Vineland Adaptive Behavior Scales (VABS-II) will be used to provide a standardized, quantifiable measure of neurobehavioral function in survivors. Poor neurobehavioral functioning is defined as a standardized VABS-II score less than 70 at 12 months. Children with a pre-cardiac arrest baseline VABS-II standardized score less than 70 will be included in the trials but will be excluded from analysis of the primary outcome. Pre-cardiac arrest baseline VABS-II information will be completed retrospectively by the caregiver (as soon as possible after enrollment to decrease retrospective bias), and the 12 month VABS-II assessment will be conducted centrally by telephone interview by the Kennedy Krieger Institute (Johns Hopkins School of Medicine, Baltimore, MD).

Differences between the two study arms with respect to this binary outcome will be evaluated using a chi-square test for each of the two THAPCA Trials separately. The rate ratio comparing survival with good neurobehavioral outcome in the hypothermia arm vs. the normothermia arm and its 95% confidence interval will also be described. Patients with a baseline VABS-II score less than 70 will be excluded from the primary analysis, but included in analyses of secondary and safety endpoints.

As all participating centers will be trained in the delivery of both arms of the study protocol, it is expected that any treatment effect should be reasonably consistent (while not uniformly so) across centers. Therefore, a secondary analysis will employ the Mantel-Haenszel test to quantify treatment effect adjusted by center. The Breslow-Day test (which we recognize will have limited power, as the number of subjects within most centers will be quite low) will be used to assess if there is evidence that treatment effect varies across center.

Missing data will be a non-negligible issue in the primary analysis. It is expected that vital status (alive or dead) will be known for almost all patients. The majority of missing data will consist of detailed neurobehavioral information. While the primary outcome analysis will use subjects with available data for the primary endpoint (complete patients), we will also report analysis results using various methods to estimate missing data including last observation carried forward (LOCF) and imputation approaches. The three month follow up will provide a better basis upon which to test our conclusions for robustness with respect to missing data. We will use the LOCF method using the three month observations, and if the three month and 12 month outcomes are highly correlated for complete patients, then the three month observation may enable a better multiple imputation-based robustness analysis.

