6.1 Screening, Enrollment, and Randomization

Clinical investigators in each site will be pediatric critical care or emergency medicine specialists; in many sites, there will be an assigned investigator in the intensive care unit and in the emergency department. The THAPCA-OH (out-of-hospital) Trial will be enhanced by close cooperation between specialists in the emergency medicine and critical care.

For cardiac arrest cases occurring in the in-hospital (IH) setting, screening will be straightforward. The assigned study physician will be notified by the clinical team as soon as possible after the ROSC/ROC occurs. In the out-of-hospital (OH) setting, the emergency medicine (EM) staff will similarly notify the assigned study physician who performs screening of cases of any arrests occurring in or coming to the emergency department. In the event of a case at another facility, the PICU or EM clinical team arranging the transport will notify the study physician for screening.

The assigned study physician will screen/review each patient for potential eligibility. A screening log will be completed for all CA patients, whether eligible or not eligible. If a patient meets inclusion/exclusion criteria for study participation, the subject's parent(s)/guardian(s) will be approached for written informed permission for the child to participate in the appropriate THAPCA trial (see Section 10.2 on page 66). Following written permission, patients will be randomized to hypothermia treatment or normothermia control therapy. Patients must be randomized within six hours of ROSC/ROC.

Note: Pregnancy is a contraindication for participation in this study. All female patients of child-bearing potential must have a negative urine or blood pregnancy test prior to enrollment.

Randomization for each trial will be stratified by clinical center and patient age group (less than 2 years, 2 to 11 years, 12 years or older). The DCC will prepare randomization schedules using randomized blocks of varying length for each of these study strata. Patients within each stratum will be randomized in a 1:1 ratio to hypothermia or normothermia. Patient randomization will be accomplished using either an Internet connection to the DCC, or an interactive telephone service.

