9.3 Secondary Analyses

Secondary endpoints of each THAPCA trial are:

1. Survival at 12 months post cardiac arrest;
2. Change in neurobehavioral function from pre-cardiac arrest baseline to 12 month measurement (VABS II);

For survivors only,

3. Neuropsychological scores at 12 month evaluation;

4. Neurological abnormality scores at 12 month evaluation.

Mortality over time will be quantified and described using standard survival analysis techniques including generation of Kaplan-Meier curves and comparing these curves between treatment arms via the logrank test. Survival at 12 months will also be evaluated as a binary outcome using the chi-square test. We expect that almost all subjects will have vital status available at 12 months.

The overall change in VABS-II from baseline to 12 months will be evaluated using a linear regression model with 12-month VABS-II as the outcome, and assigned treatment as a predictor along with baseline VABS-II score. Because the distributions may be substantially skewed, we will examine significance levels and confidence intervals for the treatment effect achieved with the nonparametric Wilcoxon rank-sum test for consistency with the findings of the parametric approach. The Wilcoxon rank-sum test will be based on ranks assigned to the differenced scores (12 month minus baseline). If outcomes unexpectedly appear to have substantially differing distribution shapes between treatment arms, resampling techniques will be used to test significance of, and estimate magnitude of, differences in median outcome between treatment arms.

Neuropsychological testing results for the Mullen Scales of Early Learning (children ≤ 5 years 8 months) will be measured as continuous outcomes. Comparison between the study groups will employ a two-sample t-test if appropriate, or alternatively, the Wilcoxon rank-sum test if basic normality assumptions are not met. As detailed in Table 3 on page 44, for patients 6 years and older there is a battery of neuropsychological tests, with separate outcome measures for each test. Comparison between groups will be based on ranks and employ the Wilcoxon rank-sum test. Patients who do not meet minimum requirements to be tested will be assigned the lowest rank for a test; patients who are tested but are unable to meet the test's basal requirements will be given the second lowest rank for that test; all other patients will receive a rank based on the actual score achieved for that test.

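### Age group is a randomisation stratum in both trials, but the primary chi-square test does not use it: a small, avoidable loss of efficiency

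*Protocol*

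**What the plan says.** Protocol section 6.1 has randomisation in each trial "stratified by clinical center and patient age group (less than 2 years, 2 to 11 years, 12 years or older". Blocking is done inside those strata: "The DCC will prepare randomization schedules using randomized blocks of varying length for each of these study strata". Allocation is 1:1 in each stratum.

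Section 9.2 names the primary test: "Differences between the two study arms with respect to this binary outcome will be evaluated using a chi-square test". It is run separately in the out-of-hospital and in-hospital trials. A rate ratio with a 95% confidence interval accompanies it, with no mention of strata. For the same endpoint, "a secondary analysis will employ the Mantel-Haenszel test to quantify treatment effect adjusted by center", followed by a Breslow-Day test across centres. Section 9.4 repeats that pair for the safety endpoints.

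The analyses in section 9.3 do not use the randomisation age groups either. The VABS-II regression, for example, has "12-month VABS-II as the outcome, and assigned treatment as a predictor along with baseline VABS-II score". The age cut at about six years in that section only selects the neuropsychological instrument. Section 9.5 allows exploratory work on patient characteristics but does not name age.

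**The concern.** Blocking within age strata keeps the arms nearly balanced on age, so the real sampling variance of the difference between arms leaves out most of the between-age variation in outcome. The plain chi-square computes its null variance as if allocation had been simple, and so keeps that variation in. When age predicts outcome, the test asks for more evidence than its nominal level requires. The design then gives up some of the precision that stratification provides.

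What is at stake is efficiency in the primary test of two trials that section 9.6 plans at 80 to 85% power for a 15-point difference. The choice of test is written into the protocol, so it cannot be treated as a detail left to the SAP.

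**Working it through.** **Inputs.** Two-sided alpha is 0.05 per trial (section 9.1). Poor-outcome rates under normothermia are 80% out-of-hospital and 65% in-hospital, with a 15-point effect (section 9.6). In terms of good outcome this is 20% v 35% and 35% v 50%. Total N for 80% power is 302 (Table 4) and 366 (Table 5). Outcome rates by age and the age distribution are not given, so they are assumed below.

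**1. Reproduce the plan's figures.** Per arm, n = [1.96√(2p̄q̄) + 0.842√(p₁q₁ + p₂q₂)]² / d², then with continuity correction n_c = (n/4)[1 + √(1 + 4/(nd))]².
- Out-of-hospital: n = 137.9, total 276; n_c = 150.95, total 302, as in Table 4.
- In-hospital: n = 169.3, total 340; n_c = 182.4, total 366, as in Table 5.

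The tables therefore assume an unstratified two-proportion comparison with continuity correction.

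**2. Chi-square against CMH by age group.** Let w_k be the share of age group k, p̄_k its rate averaged over the arms, P̄ the overall rate, and n the number per arm.
- Null variance used by the chi-square: V_chi = 2P̄(1−P̄)/n.
- Null variance used by CMH: V_str = 2Σw_k p̄_k(1−p̄_k)/n.
- Actual variance of the difference under age-stratified allocation: V₁ = Σw_k[p_Ck q_Ck + p_Hk q_Hk]/n.
- Power = Φ((d − 1.96√V_null)/√V₁), with V_chi or V_str as V_null.
- True size of the chi-square = 2[1 − Φ(1.96/√(1−R₀))], where R₀ is the between-age share of the variance at the control rates.
- Patient equivalent: N × (1 − V_str/V_chi).

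Example: out-of-hospital, N = 302, three equal age groups, odds ratio 4.5 between the extremes. Control rates are 9.5, 18.3 and 32.2%; hypothermia rates are 19.4, 33.7 and 51.9%. V_chi = 0.002641, V_str = 0.002471, V₁ = 0.002391.
- Chi-square: (0.15 − 1.96×0.0514)/0.0489 = 1.008, power 0.843.
- CMH: (0.15 − 1.96×0.0497)/0.0489 = 1.075, power 0.859.
- R₀ = 5.4%, so size = 2[1 − Φ(2.016)] = 0.044.
- Patient equivalent: 302 × 6.4% = 19.

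| Trial (N) | Age odds ratio | Chi-square size | Chi-square power | CMH power | Gain (points) | Patients |
|---|---|---|---|---|---|---|
| OH (302) | 1 | 0.050 | 0.835 | 0.835 | 0 | 0 |
| OH | 2 | 0.049 | 0.837 | 0.840 | 0.4 | 4 |
| OH | 3 | 0.047 | 0.839 | 0.848 | 0.9 | 11 |
| OH | 4.5 | 0.044 | 0.843 | 0.859 | 1.6 | 19 |
| IH (366) | 1 | 0.050 | 0.830 | 0.830 | 0 | 0 |
| IH | 2 | 0.048 | 0.832 | 0.837 | 0.5 | 7 |
| IH | 3 | 0.045 | 0.836 | 0.847 | 1.1 | 16 |
| IH | 4.5 | 0.041 | 0.840 | 0.860 | 2.0 | 29 |

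The patient column is an upper figure, because it counts the whole reduction in null variance. The chi-square already benefits from the smaller V₁. Solving the power formula for the N at which CMH only matches the chi-square gives savings of about 13 (out-of-hospital) and 20 (in-hospital) at odds ratio 4.5.

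**3. A different age mix.** With weights 50/30/20% and success rates 10/25/35%, P = 0.195, P(1−P) = 0.1570 and Σw p(1−p) = 0.1468. The reduction is 1 − 0.1468/0.1570 = 6.5%. Rates of 15/22/28% give 1.7%, and 25/38/50% give 4.3%. The range is the same.

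**4. Simulation check.** Out-of-hospital, N = 300, blocks of 2 and 4, 30 centres assumed, 6000 runs per setting.
- Between-centre SD 0.5 and age log odds ratio 1.5: chi-square size 0.037 and power 0.845; CMH by age 0.859; CMH by full centre-by-age cells 0.837.
- Nothing prognostic: chi-square 0.834, CMH by age 0.832, full cells 0.788.

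**The case against.** The best defence is that nothing is invalid. The chi-square controls type I error, and the crude rate ratio estimates a legitimate marginal effect. The possible gain is small and depends entirely on an age effect that the protocol does not report. The 10/25/35% case implies an odds ratio of (0.35/0.65)/(0.10/0.90) = 4.8, which is strong. The VABS-II is also normed for age (section 6.6.1), which may weaken any age effect among survivors. All of this stands, and it limits the point to efficiency.

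A reader might infer that the mismatch leaves the out-of-hospital trial short of power, since Table 4 puts 250 to 300 patients at roughly 71 to 80%. The documents do not support that link. Table 4 includes a continuity correction that section 9.2 does not specify. For an uncorrected chi-square the same numbers give about 76 to 83%. The correction alone is worth 302 − 276 = 26 patients, more than the largest out-of-hospital gain found here.

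A reader might also infer that no analysis anywhere uses age, or that stratification is ignored altogether. Neither can be said. Centre is used in the secondary analysis, and supporting age-adjusted analyses may be in a SAP that is not at hand. What the protocol fixes is the primary test and one centre-only adjustment.

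Finally, analysing exactly as randomised might seem to call for centre-by-age strata. Section 9.2 itself expects few patients in most centres, and the simulation shows that such sparse cells can cost power.

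**Conclusion.** The mismatch is real, and the protocol itself fixes it: age group is a randomisation stratum, while the primary test and its only stated adjusted companion leave it out. The consequence is a slightly conservative test (size about 0.041 to 0.050) and a loss of about 0 to 2 points of power. That is equivalent to 0 to about 19 patients out-of-hospital and 0 to about 29 in-hospital at most. It is not a validity error and does not inflate type I error. If age is not prognostic, nothing is lost.

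These figures rest on assumed odds ratios of 1 to 4.5 between the extreme age groups, an assumed age mix, the design rates of section 9.6, and arms that stay balanced by age among the patients analysed. Loss to follow-up and the exclusion of children with a baseline VABS-II below 70 make that balance approximate. The direction is firm; the size is not known.

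**What to change.** Before unblinded data are seen, amend section 9.2:
- Make the primary test in each trial a CMH test stratified by the three randomisation age groups, reported with the Mantel-Haenszel rate ratio and its 95% confidence interval.
- Keep the plain chi-square as a sensitivity analysis.
- Leave the centre-adjusted Mantel-Haenszel analysis as the secondary analysis, and do not stratify on full centre-by-age cells.
- Use the same primary test at the interim looks in section 9.7, so that the boundaries apply to one statistic throughout.

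The cost is a sentence or two in the protocol and matching text in the SAP. No extra data or patients are needed. With only three strata, the cost in power is essentially nil if age turns out not to matter (0.835 for either test at N = 302).

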2.3 Rationale for Current Study

2.3.1 Different Etiology of Cardiac Arrest in Children and Adults

A recent survey ranked the efficacy of TH therapy as one of the most important unanswered questions related to pediatric resuscitation.³⁶ Since no effective interventions for neuroprotection following pediatric CA exist currently, some initially recommended extrapolation of adult study findings to pediatric practice.^{27, 28, 37} However, an expert committee concluded that it was important to validate the adult TH for CA findings in infants and children,^{38, 39} because of differences in the pathophysiology of CA between populations. For example, mechanisms of CA in pediatrics vs. adults differ, especially in the OH setting. Asphyxia with a period of hypoxia followed by later ischemia is the common sequence leading to CA in pediatrics; whereas, sudden cardiac arrhythmias cause CA more commonly in adults. In children, CA occurs with asystole and/or pulseless electrical activity (PEA) being the most common presenting cardiac rhythms, while in adults a primary cardiac arrhythmia, usually ventricular fibrillation (VF) or pulseless ventricular tachycardia, leads to CA. Survival from pediatric VF is reported to be much greater than survival from pediatric asystole.²⁰

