6.6.3 Neuropsychological Testing

In children, duration of cardiac arrest⁴⁹ and of circulatory arrest during heart surgery⁵⁸ have been associated with lower performance on measures of overall cognitive ability. Additionally, anoxic brain injury often significantly impacts specific neuropsychological skills, including attention, memory, executive functioning, processing speed and motor functioning.^{59, 60} To more fully describe these cognitive outcomes and identify subtler but significant impairments, a brief battery of neuropsychological testing will be administered 12 to 16 months post arrest, by designated psychologists at each study site. Measures were chosen that are sensitive to brain injury, have adequate normative data for the age range, plus good reliability and validity. For all children 5 years 8 months or younger, the Mullen Scales of Early Learning will be employed at 12 months post arrest to obtain a measure of overall cognitive functioning. Since the Mullen only has available data through age 5 8/12th years, for children 5 9/12th through 5 11/12th years, testing will be delayed until they are six years old, which may be as late as 16 months post arrest.

For children 6 years of age or older neuropsychology testing will be administered if the child usually "follow instructions" (question 10, VABS-II Receptive Communication) or usually "point or gesture to indicate preference" (question 10, VABS-II Expressive Communication), or have higher level communication skills. For these children, the 2-subtest version (Vocabulary and Matrix Reasoning) of the Wechsler Abbreviate Scale of Intelligence will be administered to obtain a measure of general cognitive functioning (estimated full scale IQ score). In addition, a battery of specific neuropsychological measures to assess processing speed, attention, learning

and memory, executive functioning (ability to plan, organize, and engage in goal directed behavior), and visual motor functioning will be administered to these children

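### The primary chi-square is valid but uses neither the age-group stratum nor the arrest characteristics the protocol links to outcome, which gives up power chiefly in the out-of-hospital trial

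*Protocol*

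**What the plan says.** Section 9.2 compares the arms on the binary primary endpoint (alive with a 12-month VABS-II of at least 70, among children whose baseline score was not below 70). Differences "with respect to this binary outcome will be evaluated using a chi-square test", run in each trial on its own, with a rate ratio and its 95% confidence interval. The only adjusted analysis of this endpoint is also in 9.2: "a secondary analysis will employ the Mantel-Haenszel test to quantify treatment effect adjusted by center". Section 9.1 sets the error rate: "the alpha level for analysis of each trial is 0.05" and "All tests will be two-tailed". Regression on factors associated with outcome appears only in section 9.5, as exploratory work.

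Section 6.1 stratifies randomization by clinical center and by three age groups. Arrest characteristics are not strata.

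Two background statements bear on prognosis. Section 2.3.1: "Survival from pediatric VF is reported to be much greater than survival from pediatric asystole". Section 6.6.3 says that, in children, duration of cardiac arrest and of circulatory arrest during heart surgery "have been associated with lower performance on measures of overall cognitive ability". Section 8.2 lists the trial's baseline data as including "hospital and PICU admission information, cardiac arrest information, vital signs"; it does not itemise rhythm or duration. Section 2.4 does itemise both, but for the planning cohort.

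**The concern.** When a baseline variable predicts a binary outcome, a comparison that ignores it leaves explainable variation in the error term. The estimate is less precise and the power lower than the same children could give. The protocol ties rhythm to one component of its endpoint (survival) and arrest duration to something close to the other (cognition). It also stratifies on age but states no primary-endpoint analysis that uses age. Elsewhere it accepts baseline adjustment: the VABS-II change analysis in section 9.3 includes the baseline score.

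At stake is power in the out-of-hospital trial, where section 9.6 claims 80 to 85% for a 15-point effect on an effective size of 250 to 300.

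**Working it through.** **Inputs.** Control-arm poor-outcome rates of 80% (out-of-hospital, OH) and 65% (in-hospital, IH), a 15-point effect, and effective sizes of 250–300 (OH) and 400–500 (IH), all from section 9.6. Two-sided alpha of 0.05 from section 9.1. Required sizes from Tables 4 and 5.

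**Reproducing the plan's own figures.** Per arm, n = [1.96·√(2·p̄(1−p̄)) + z_power·√(p₁(1−p₁)+p₂(1−p₂))]² / d². The continuity correction is n_c = (n/4)·[1+√(1+4/(n·d))]².

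- OH, 0.80 vs 0.65, 80% power: n = 137.9 (total 276); n_c = 150.95, so 151 per arm and 302 in total. Table 4 says 302.
- IH, 0.65 vs 0.50, 80% power: n = 169.3 (total 340); n_c = 182.4, so 183 per arm and 366 in total. Table 5 says 366.

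Both are exact with the continuity correction.

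**Power at the expected sizes.** Without correction, power = Φ{[d·√n − 1.96·√(2·p̄(1−p̄))] / √(p₁(1−p₁)+p₂(1−p₂))}. For OH at 250 (n = 125): (1.677 − 1.238)/0.622 = 0.706, so 76.0%.

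| Trial, total N | No correction | Continuity-corrected, as in the tables |
|---|---|---|
| OH 250 | 76.0% | 71.3% |
| OH 300 | 83.2% | 79.7% |
| IH 400 | 86.2% | 83.8% |
| IH 500 | 92.6% | 91.3% |

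By the tables' method, OH reaches 80% only at the very top of its range (302 needed). IH exceeds 80% throughout (366 needed, 400–500 expected). At the illustrative final level of 0.0426 (section 9.7), uncorrected OH power is 73.8% at 250 and 81.4% at 300.

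**What adjustment could add.** The documents give no prognostic strength, so the share of outcome variation explained, R², is assumed. Effective size is taken as N/(1−R²), with power uncorrected.

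| R² (assumed) | OH 250 acts like | OH 250 | OH 300 | IH 400 |
|---|---|---|---|---|
| 0 | 250 | 76.0% | 83.2% | 86.2% |
| 0.05 | 263 | 78.1% | 85.1% | 87.8% |
| 0.10 | 278 | 80.3% | 86.9% | 89.5% |
| 0.15 | 294 | 82.5% | 88.7% | 91.1% |
| 0.20 | 313 | 84.7% | 90.5% | 92.6% |

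**Cross-check by simulation.** Chi-square was compared with a logistic Wald test over 4,000 runs per scenario, with a normally distributed baseline score and the marginal rates held fixed. For OH at 250 the chi-square gave about 76–77%. Adjustment gave 78.3%, 80.8% and 84.2% for scores with AUC 0.64, 0.71 and 0.78 (variance reductions of 4.5%, 10.3% and 19.3%). A useless score gained nothing: 76.1% unadjusted, 75.8% adjusted. A binary rhythm variable alone, assumed to have 10–20% prevalence of the favourable rhythm and an odds ratio of 3–5, removed only about 3–10% of the OH variance.

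**How much model the data can carry.** At OH 250 under the target effect, good outcomes number 125×0.20 + 125×0.35 ≈ 69. At a 10% information look, about 25 children would give about 7.

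**The case against.** The strongest reply is that this is a design preference. The chi-square is simple, matches the sample-size method and holds its type I error. That stands. A reader might infer that chance imbalance in rhythm or duration would bias the primary result or invalidate the test. The documents do not support that: under randomization the test's error rate already covers chance imbalance, and what is lost is efficiency.

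Three further limits stand.

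- A reader might infer that the protocol commits to collecting rhythm and duration at baseline. Section 8.2 names only cardiac arrest information in general. Capture is a fair inference, since eligibility depends on at least two minutes of compressions and the planning cohort recorded both items, but it is not stated. Section 2.3.2 says only 31% of out-of-hospital arrests are witnessed, so timing may be incomplete in the trial that most needs it.
- The prognostic statements concern survival and cognitive test performance. Neither gives an effect on the composite endpoint, or in children already selected for sustained circulation, ventilation and a low motor score. Section 2.3.1 also says asystole and pulseless electrical activity are the most common presenting rhythms in children, so a shockable/non-shockable split would be uneven.
- A reader might infer that both trials are short of power. Only OH is.

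A model with a term for every center would be sparse: section 9.2 itself expects few subjects in most centers. That argues for a leaner model. It does not remove the case for adjusting.

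**Conclusion.** The point holds as an efficiency weakness that the protocol fixes in its own text, not as an error in the test. The unadjusted primary analysis forgoes whatever age group, initial rhythm and arrest duration could contribute. This matters mainly for OH; IH would gain precision from adequate power. The size cannot be fixed from the documents. On an assumed R² of 0 to 0.20, OH power at 250 runs from 76% to 85% without continuity correction, and R² = 0.10 is worth about 28 children. Those figures rest on the section 9.6 outcome rates, the N/(1−R²) approximation and near-complete covariates. Adjustment therefore cannot be relied on to make the 80 to 85% power claim true across the OH range.

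**What to change.** Before the first interim look:

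1. Confirm that initial rhythm and duration of chest compressions are captured within the baseline arrest data.
2. Prespecify as primary, in each trial, a comparison adjusted for age group, initial rhythm and duration of chest compressions. Report the standardized (marginal) risk difference and risk ratio with robust confidence intervals.
3. Do not enter center as fixed effects. Keep the center Mantel-Haenszel test as secondary.
4. Handle missing baseline covariates by a missing category or simple imputation, so that no child is dropped.
5. State that the unadjusted test is used at early looks with too few events to fit the model.
6. Report the unadjusted chi-square as supportive.

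The cost is analysis wording, plus a data-form check for rhythm and duration. The downside is a model-based primary estimate, with little gain if the covariates prove weakly prognostic. The planning cohort in section 2.4 holds rhythm, CPR duration, survival to discharge and PCPC/POPC, so the likely strength can be gauged before the covariate list is fixed.
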